#### 3.3 Inclusion of Women and Minorities

Both men and women of all races and ethnic groups are eligible for this trial.

# 4. REGISTRATION AND RANDOMIZATION PROCEDURES

# 4.1 General Guidelines for DF/HCC Institutions

Institutions will register eligible participants in the Clinical Trials Management System (CTMS) OnCore. Registrations must occur prior to the initiation of any protocol-specific therapy or intervention. Any participant not registered to the protocol before protocol-specific therapy or intervention begins will be considered ineligible and registration will be denied.

An investigator will confirm eligibility criteria and a member of the study team will complete the protocol-specific eligibility checklist.

The eligibility checklist(s) and all pages of the consent form(s) will be faxed to the ODQ at [contact] or emailed to their central or designee. The ODQ will (a) review the eligibility checklist, (b) register the participant on the protocol, and (c) randomize the participant.

Randomization can only occur during ODQ business hours (8:30am - 5pm Eastern Time, Monday through Friday excluding holidays).

An email confirmation of the registration will be sent to the Overall PI, study coordinator(s) from the Lead Site, treating investigator and registering person immediately following the registration and/or randomization.

An email confirmation of the randomization assignment will be sent to the registering site's study pharmacist and the lead site's Unblinded Contact (or back-up) immediately following the registration and/or randomization.

Following registration, participants may begin protocol-specific therapy and/or intervention. Issues that would cause treatment delays should be discussed with the Overall Principal Investigator (PI). If the subject does not receive protocol therapy following registration, the subject must be taken off-study in the CTMS (OnCore) with an appropriate date and reason entered.

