# 5.7.3 Prohibited Concomitant Medications

Participants are prohibited from receiving the following therapies during the Screening and Treatment Phase of this trial:

- Anti-cancer systemic chemotherapy or biological therapy (bevacizumab or biosimilar can be used to control effects of edema and mass effect. A washout period of 2 weeks between each VB-111 and bevacizumab or biosimilar dose is recommended)
- Immunotherapy not specified in this protocol
- Chemotherapy not specified in this protocol
- Investigational agents other than VB-111
- Radiation therapy
- Systemic glucocorticoids for any purpose other than to modulate symptoms from an adverse event of suspected immunologic etiology or to control cerebral edema. The use of physiologic doses of corticosteroids may be approved after consultation with the Overall Principal Investigator.

Participants who, in the assessment by the treating investigator, require the use of any of the aforementioned treatments for clinical management should be removed from the trial. Participants may receive other medications that the treating investigator deems to be medically necessary.

The Exclusion Criteria describes other medications which are prohibited in this trial unless otherwise described (e.g. bevacizumab or biosimilar and Group C study treatment). There are no prohibited therapies during the Post-Treatment Follow-up Phase.

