# 5.10 Long-Term Follow-Up and Study Completion

After documented disease second progression, each participant will be followed by telephone or medical record review for overall survival until they meet criteria for removal from study as detailed below.

Participants will be removed from study when any of the following criteria apply:

- Lost to follow-up
- Withdrawal of consent
- Death

The reason for taking a participant off study, and the date the participant was removed, must be documented in the case report form (CRF). In addition, the study team will ensure Off Treatment/Off Study information is updated in OnCore in accordance with DF/HCC policy REGIST-101. Lastly, the study team will ensure the participant's status is updated in OnCore in accordance with REGIST-OP-1.

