## **13.2** Definitions of Analysis Sets

- The Full Analysis Set (FAS) population will serve as the population for the analysis of primary efficacy endpoint TIL density in this study. The FAS population consists of all participants within each cohort who have received a preoperative dose of VB-111/placebo and had a surgery.
- The intention to treat (ITT) population is defined as all randomized participants. The ITT population will be used for secondary efficacy endpoints (PFS6, OS).
- The All Participants as Treated (APaT) population will be used for the analysis of safety data in this study. The APaT population consists of all allocated participants who received at least one dose of study treatment. At least one laboratory or vital sign measurement obtained subsequent to at least one dose of study treatment is required for inclusion in the analysis of each specific parameter. To assess change from baseline, a baseline measurement is also required.

A randomized, placebo controlled phase II, surgical trial to evaluate early immunologic pharmacodynamic parameters for the viral cancer therapy ofranergene obadenovec (VB-111) in patients with surgically accessible recurrent/progressive glioblastoma Version 3.0 February 18, 2021

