# 3.7 DF/HCC Multi-Center Protocol Registration Policy

Eligible participants will be entered on study centrally at the DFCI Coordinating Center (by a Coordinating Center specialist, if participant is at a non-DF/HCC site). Registration must occur prior to the initiation of therapy. Any participant not registered to the protocol before treatment begins will be considered ineligible and registration will be denied.

A qualified member of the study team will confirm eligibility criteria and complete the protocol-specific eligibility checklist.

Issues that would cause treatment delays should be discussed with the Principal Investigator. If a participant does not receive protocol therapy following registration, the participant's protocol status must be changed. A Coordinating Center specialist should be notified of cancellations - or any status changes - as soon as possible.

In order to register a participant onto study, the following must be done:

- Obtain written informed consent from the participant prior to the performance of any study related procedures or assessments.
- Complete the protocol-specific eligibility checklist using the eligibility assessment documented in the participant's medical/research record.
  - To be eligible for registration to the study, the participant must meet each inclusion and exclusion criteria listed on the eligibility checklist.

**Reminder:** Confirm eligibility for ancillary studies at the same time as eligibility for the treatment study. Registration to both treatment and ancillary studies will not be completed if eligibility requirements are not met for all studies.

After participant has been registered to study:

- 1. A separate Multi-Center Coordinating Center specialist (19-792 Unblinded Contact, or back-up) will inform the participating site's pharmacy contact of the successful randomization via Fax or email, to include Applicable treatment arm assignment, and requests a confirmation
- 2. Site's pharmacy contact confirms receipt of patient's assignment via email to 19-792 Unblinded Contact (or back-up)
- 3. The Designee (Multi-Center Coordinating Center specialist) emails Site Team to confirm pharmacy contact has received patient's randomization assignment

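### The off-study wording in Sections 4.1 and 4.3, and less clearly 5.7.3, conflicts with following all randomized participants for OS and PFS6

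*Combined protocol and SAP*

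**What the plan says.** **Rules that end participation.** Section 4.1 (DF/HCC sites) states: "If the subject does not receive protocol therapy following registration, the subject must be taken off-study in the CTMS (OnCore"). Section 4.3 gives the same instruction to the other sites. Section 5.7.3 says that participants who "require the use of any of the aforementioned treatments for clinical management should be removed from the trial".

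**Rules that require follow-up.** Section 13.2: "The intention to treat (ITT) population is defined as all randomized participants", and "The ITT population will be used for secondary efficacy endpoints (PFS6, OS"). Sections 1.1 and 5.1 follow all participants for survival, by telephone or record review, until death, withdrawal of consent or the end of the study. Section 5.10 introduces its list with "Participants will be removed from study when any of the following criteria apply", and the list has three entries: loss to follow-up, withdrawal of consent and death.

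**A third wording.** For the untreated participant, Appendix B Section 3.7 says only: "If a participant does not receive protocol therapy following registration, the participant's protocol status must be changed".

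**The concern.** A participant who is randomized and never dosed, or who comes to need a prohibited therapy, is in the ITT set. Neither event is among the Section 5.10 reasons for leaving the study, yet 4.1 and 4.3 order the first off-study and 5.7.3 can be read as doing the same to the second.

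If a site stops contact on that basis, the outcome is not collected and may not be recoverable later. Failure to start treatment and need for other anticancer therapy may both be related to prognosis, so the missing outcomes need not resemble the observed ones. OS and PFS6 would then be labelled ITT while resting on a selected subset.

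**Working it through.** The plan gives no figure for this point: it states neither a dropout rate nor an expected number of untreated participants. The check is therefore mainly a comparison of passages, with arithmetic for size.

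**1. Is an untreated registrant in ITT?** Yes. Under Section 4.1 the data office will "register the participant on the protocol, and (c) randomize the participant" in one sequence, and ITT is all randomized participants.

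**2. What is a site told to do?**
- Untreated participant: 4.1 and 4.3 say off-study; Appendix B 3.7 says change the status; 1.1 and 5.1 say follow for survival; 5.10 does not list non-treatment as a reason to leave.
- Participant needing a prohibited therapy: 5.7.3 says removed from the trial; Section 5.7 says discontinuation of trial therapy may be required; 5.10 does not list it.

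Sections 5.8 and 5.10 treat stopping protocol therapy and leaving the study as different statuses, so the choice of word matters.

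**3. Do the follow-up rules reach the never-treated?** Disease follow-up in Section 5.9 and calendar footnote 9 covers participants who discontinue treatment. Survival follow-up in 13.1.1 is described as continuing after progression or drug discontinuation. Someone who never started is clearly reached only by the general sentence in 1.1 and 5.1, which is the sentence that 4.1 and 4.3 contradict.

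**4. What would the analysis do?** Section 13.4 censors participants without efficacy or survival data at Day 1. In a Kaplan-Meier estimate such a person contributes essentially no follow-up. PFS6 is tested as a binomial proportion, for which a Day 1 censoring has no defined value. PFS6 is also timed from surgery (13.1.1), so an ITT member without surgery has no time origin.

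**5. Size.** Section 5.6 recruits until each arm has 15 evaluable participants, and a never-dosed participant is not evaluable. With m such participants the ITT arm has at least 15 + m members:
- Weight of one participant = 1/(15 + m), at most 1/16 = 6.25 points.
- If x of the 15 evaluable are progression-free, PFS6 lies between x/(15 + m) and (x + m)/(15 + m).

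x and m are assumed here for illustration:

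| x of 15 | m unfollowed | Excluded | All failures | All successes |
|---|---|---|---|---|
| 2 | 1 | 13.3% | 2/16 = 12.5% | 3/16 = 18.8% |
| 2 | 2 | 13.3% | 2/17 = 11.8% | 4/17 = 23.5% |
| 5 | 1 | 33.3% | 5/16 = 31.3% | 6/16 = 37.5% |
| 5 | 2 | 33.3% | 5/17 = 29.4% | 7/17 = 41.2% |
| 5 | 4 | 33.3% | 5/19 = 26.3% | 9/19 = 47.4% |

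For the whole trial, assume that 5%, 10%, 15% or 20% of randomized participants are not evaluable and are replaced. Then 45/(1 − u), rounded up, gives an ITT set of 48, 50, 53 or 57, with 3, 5, 8 or 12 outside the evaluable set. Only the never-treated among them fall under 4.1 or 4.3.

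**6. Can loss differ by group through knowledge of assignment?** Not before surgery. The first dose is due within 5 days of randomization (5.3.1), investigator and participant are blinded pre-operatively (5.4), and assignment is released after surgery is confirmed (Appendix B 3.7.4). After surgery treatment is open, so the argument applies only to removals under 5.7.3 at that stage.

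**The case against.** The strongest reply is that the protocol's intent is clear. Sections 1.1 and 5.1 follow everyone for survival, 5.9 continues disease follow-up after discontinuation for reasons other than progression, and 13.1.1 continues survival follow-up after the drug is stopped. On 5.7.3, the same section adds "There are no prohibited therapies during the Post-Treatment Follow-up Phase", Section 5.7 speaks of stopping trial therapy, and the calendar collects post-treatment therapies through long-term follow-up. In that context, removal from the trial is probably loose wording for off treatment. Section 5.7.3 also excepts bevacizumab or biosimilar for edema and mass effect, so that use does not trigger removal. Finally, the 4.1 instruction concerns a status in the registration system, governed by policies that are not part of these documents; whether that status ends vital-status review cannot be established from them.

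Much of this stands, and it rules out three stronger readings.
- A reader might infer that the ITT set cannot be followed. The documents do not support that: only a subset is touched, and several passages require its follow-up.
- A reader might take 1/15 = 6.7 points as the weight of each lost participant. Fifteen is the evaluable count, and never-dosed participants come on top of it.
- A reader might extend the open-label argument to the never-dosed. They are lost while assignment is still blinded.

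The reply does not remove the mandatory wording in 4.1 and 4.3, or the gap in 5.9 for participants who never start. Section 11.2.4 counts failure to return because of death or deterioration as progression, but that helps only if the participant is still being assessed.

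**Conclusion.** The concern holds as an internal contradiction. Sections 4.1 and 4.3, and less clearly 5.7.3, conflict with the ITT analysis in 13.2, with survival follow-up of all participants in 1.1 and 5.1, and with the off-study list in 5.10. Followed literally, 4.1 and 4.3 allow the outcomes of never-treated ITT members to go uncollected.

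The number affected is unknown. The ceiling of 6.25 points of PFS6 per never-dosed participant assumes that replacement does reach 15 evaluable per arm. That the resulting censoring is informative is plausible but not shown. The effect is confined to secondary endpoints, because the primary TIL density analysis uses the FAS. In arms of about 15, even one or two unfollowed participants would noticeably widen what can be said about PFS6.

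**What to change.** - In 4.1, 4.3 and 5.7.3, record these participants as off treatment rather than off study, and align Appendix B 3.7 with that. This changes only follow-up status, not who stops treatment.
- State that every randomized participant, treated or not, stays in survival follow-up through the existing telephone or record-review contacts, and in progression follow-up where it can be assessed. Extend 5.9 to those who never start.
- State that only the 5.10 criteria end follow-up.
- In 13.1.1 or 13.4, state how ITT members without surgery count in PFS6, for example by timing it from randomization or by counting them as not progression-free. Fix the choice before outcomes are reviewed.

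The cost is a wording amendment and a few additional follow-up contacts. The sample size and the primary analysis do not change.

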### 4.2 **Registration Process for DF/HCC Institutions**

Applicable DF/HCC policy (REGIST-101) must be followed. And refer to Appendix B (DSMP), Section 3.7.

# 4.3 General Guidelines for Other Investigative Sites

Eligible participants will be entered on study centrally at the Dana-Farber Cancer Institute by DFCI Coordinating Center staff. All sites should contact the DFCI Coordinating Center at Neuro [contact] to verify slot availabilities. A list of the required forms for registration can be found in Appendix B (DSMP), Section 3.7.

Following registration, participants must begin protocol therapy within 5 days. Issues that would cause treatment delays should be discussed with the Overall PI. If the subject does not receive protocol therapy following registration, the subject must be taken off-study in the CTMS (OnCore) with an appropriate date and reason entered.

# 4.4 Registration Process for Other Investigative Sites

Refer to Appendix B (DSMP), Section 3.7.

# 4.5 Unblinding and Step 2 Registration for All Sites

Refer to Appendix B (DSMP), Section 3.7.4.

# 5. TREATMENT PLAN

This is a randomized, controlled, blinded, phase II, surgical trial to evaluate early immunologic pharmacodynamic parameters for the viral cancer therapy VB-111 in participants with surgically accessible recurrent/progressive glioblastoma (rGBM).

## 5.1 Treatment Regimen

Participants will be screened for eligibility up to 14 days prior to randomization. They will be sequentially randomized to one of three groups in a 1:1:1 ratio of the Neoadjuvant/Adjuvant arm (Group A), Adjuvant arm (Group B), and Control arm (Group C).

Group A (Neoadjuvant/adjuvant): Fifteen participants will receive VB-111 at 1x10^13 VPs intravenously 21±7 days prior to surgery. Tumor samples will be obtained at time of surgery, and tissue (fresh, frozen and FFPE) will be processed to achieve primary, secondary and exploratory objectives. Upon recovering from surgery (within 28-35 days after surgery), participants will resume single agent intravenous VB-111 every 6 weeks until tumor progression is supported by two consecutive time points of tumor growth (based on RANO criteria) or adverse event requiring discontinuation of study drug. Upon initial evidence of contrast-enhancing progression, and if clinically stable, participants may continue with VB-111 infusions. Bevacizumab or biosimilar may be used as supportive care if clinically indicated. Blood samples will be obtained as pharmacodynamics markers throughout the study. Dose holds and symptomatic management will occur based on preset adverse event determination. DLTs will not be determined. The toxicity evaluation period will begin with registration and extend to 30 days after the last treatment day. Participants will be followed for MRI changes, clinical exam and steroid doses from the registration period until the second progression. After tumor progression is confirmed on the second consecutive MRI, VB-111 will stop and participants will be followed every 3 months for vital status until death.

**Group B** (Adjuvant): Fifteen participants will receive Placebo intravenously 21±7 days prior to surgery. Tumor samples will be obtained at time of surgery, and tissue (fresh, frozen and FFPE) will be processed to achieve primary, secondary and exploratory objectives. Upon recovering from surgery (within 28-35 days after surgery), participants will receive single agent intravenous VB-111 every 6 weeks until tumor progression is supported by two consecutive time points of tumor growth (based on RANO criteria) or adverse event requiring discontinuation of study drug. Upon evidence of contrast-enhancing progression, and if clinically stable, participants may continue with VB-111 infusions. Bevacizumab or biosimilar may be used as supportive care if clinically indicated. Blood samples will be obtained as pharmacodynamics markers throughout the study. Dose holds and symptomatic management will occur based on preset adverse event determination. DLTs will not be determined. The toxicity evaluation period will begin with registration and extend to 30 days after the last treatment day. Participants will be followed for MRI changes, clinical exam and steroid doses from the registration period until the second progression. After tumor progression is confirmed on the second consecutive MRI, VB-111 will stop and participants will be followed every 3 months for vital status until death.

**Group C** (Control): Fifteen participants will receive Placebo intravenously  $21\pm7$  days prior to surgery. Tumor samples will be obtained at time of surgery, and tissue (fresh, frozen and FFPE) will be processed to achieve primary, secondary and exploratory objectives. Upon recovering from surgery (within 28-35 days after surgery), participants will receive standard of care treatment until evidence of progression as determined in Group A and Group B.

Since there are various treatment alternatives for recurrent glioblastoma, the Investigator may choose any of the single agent treatments for participants randomized to the standard of care arm listed in Table 1 for the control treatment arm. When selecting the treatment, the Investigator should take into consideration the participant's prior treatment (e.g. participants who had received prior lomustine should not receive it again) and clinical status following surgical resection of the tumor.

Single Agent Treatment	Dose
Lomustine	(Oral [PO]) 110mg/m2 every 6 weeks is suggested
Temozolomide	(PO or IV) Initial dose of 150mg/m2 once daily for 5 consecutive days per 28-day treatment cycles, may be increased to 200mg/m2 once daily for 5 consecutive days in the following 28-day treatment cycles
Temozolomide metronomic	(PO) 50mg/m2 once daily continuously
Bevacizumab or Biosimilar	(IV) 10mg/kg every 2 weeks

Table 1: Investigator's Choice Single Agent Standard of Care Treatments.

After recovering from surgery, participants will be evaluated every 6 weeks with radiographic imaging to assess response to treatment. The Response Assessment in Neuro-Oncology (RANO) criteria will be used as the efficacy endpoint of response rate. A modified RANO (iRANO) (as described in Section 11.4) will be used to evaluate response and progression in an exploratory fashion due to the tumor response patterns seen with immunotherapy treatment (e.g., tumor flare). Adverse events will be monitored throughout the trial and graded in severity according to the guidelines outlined in the NCI CTCAE version 5.0. Treatment with study therapy will continue until documented disease progression supported by two consecutive time points of tumor growth, unacceptable adverse event(s), intercurrent illness that prevents further administration of treatment, investigator's decision to withdraw the participant, participant withdraws consent, pregnancy of the participant, noncompliance with trial treatment or procedure requirements, completion of 24 months of study therapy, or administrative reasons. After the end of treatment, each participant will be followed for 30 days for adverse event monitoring and 90 days for serious adverse event reporting. Participants who discontinue treatment for reasons other than disease progression will have post-treatment follow-up of disease status approximately every 8 weeks until disease progression, withdrawing consent, or becoming lost to follow-up. All participants will be followed by telephone contact or medical record review for overall survival until death, withdrawal of consent, or the end of the study, whichever comes first.

The investigator shall take responsibility for and shall take all steps to maintain appropriate records and ensure appropriate supply, storage, handling, distribution and usage of trial treatments in accordance with the protocol and any applicable laws and regulations.

